4.6.8.1 Data Collection Methods for Clinical Outcome Assessments

PRO questionnaires will be collected on paper by the mHCP at the patient's home during the visit as per scheduled of activities (Appendix 1). The completion of the questionnaire will be performed independently by patients at the start of the visit, before discussion with patients about any results, or health status, and prior to any other study assessments that could bias patient's responses to ensure validity of the questionnaire is not compromised and that data quality meets regulatory requirements.

The PRO questionnaires will be collected at baseline and subsequently as per schedule of activities until the treatment discontinuation visit, withdrawn of consent, death, or study termination, whichever occurs first.

PRO questionnaires will be made available in different languages and will be provided by the Sponsor.

Patients should be given the following instructions for completing PRO questionnaires at home:

- Patients should complete the instruments in a quiet area with minimal distractions and disruptions.
- Patients should answer questions to the best of their ability; there are no right or wrong answers.
- Patients should not obtain advice or help from others (e.g., mHCP, family members, or friends) when completing the instruments.

4.6.8.2 Description of Clinical Outcome Assessment Instruments EQ-5D-5L

The EQ-5D-5L is a validated self-reported health status questionnaire that is used to calculate a health status utility score for use in health economic analyses (EuroQol Group 1990; Brooks 1996; Herdman et al. 2011; Janssen et al. 2013) (see Appendix 7).

Alectinib—F. Hoffmann-La Roche Ltd

There are two components to the EQ-5D-5L: a five-item health state profile that assesses mobility, self-care, usual activities, pain/discomfort, and anxiety/depression, as well as a VAS that measures health state. The EQ-5D-5L is designed to capture the patient's current health status. Published weighting systems allow for creation of a single composite score of the patient's health status. The EQ-5D-5L takes approximately 3 minutes to complete. It will be used in this study for informing pharmacoeconomic evaluations.

EORTC QLQ-C30

The EORTC QLQ-C30 is a validated, reliable self-reported questionnaire (Aaronson et al. 1993) (see Appendix 8). It consists of 30 questions that assess five aspects of patient functioning (physical, emotional, role, cognitive, and social), eight symptom scales (fatigue, nausea and vomiting, pain, dyspnea, insomnia, appetite loss, constipation and diarrhea) and global health/quality of life, with a recall period of the previous week. The EORTC QLQ-C30 module takes approximately 10 minutes to complete.

4.6.9 Optional Samples for Research Biosample Repository

4.6.9.1 Overview of the Research Biosample Repository

The Research Biosample Repository (RBR) is a centrally administered group of facilities used for the long-term storage of human biological specimens, including body fluids, solid tissues, and derivatives thereof (e.g., DNA, RNA, proteins, peptides). The collection, storage, and analysis of RBR samples will facilitate the rational design of new pharmaceutical agents and the development of diagnostic tests, which may allow for individualized drug therapy for patients in the future.

Samples for the RBR will be collected from patients who give specific consent to participate in this optional research. RBR samples will be analyzed to achieve one or more of the following objectives:

- To study the association of biomarkers with efficacy or disease progression
- To identify safety biomarkers that are associated with susceptibility to developing adverse events or can lead to improved adverse event monitoring or investigation
- To increase knowledge and understanding of disease biology and drug safety
- To study drug response, including drug effects and the processes of drug absorption and disposition
- To develop biomarker or diagnostic assays and establish the performance characteristics of these assays

4.6.9.2 Approval by the Institutional Review Board or Ethics Committee

Collection, storage, and analysis of RBR samples is contingent upon the review and approval of the exploratory research and the RBR portion of the Informed Consent Form by the IRB/EC and, if applicable, an appropriate regulatory body. Only if the IRB/EC has

Alectinib—F. Hoffmann-La Roche Ltd

granted approval for RBR sampling, this section of the protocol (Section 4.6.9) will be applicable.

4.6.9.3 Sample Collection

The following samples will be stored in the RBR and used for research purposes, including, but not limited to, research on biomarkers related to ALK-positive solid tumors, diseases, or drug safety:

• Leftover plasma collected for biomarkers and leftover tissue samples (with the exception of remaining archival tissue blocks, which will be returned) and any derivatives thereof (e.g., DNA, RNA, proteins, peptides)

The above samples may be sent to one or more laboratories for analysis of germline or somatic variants via whole genome sequencing (WGS), whole exome sequencing (WES), or other genomic analysis methods. Genomics is increasingly informing researcher's understanding of disease pathobiology. WGS and WES provide a comprehensive characterization of the genome and exome, respectively, and, along with clinical data collected in this study, may increase the opportunity for developing new therapeutic approaches or new methods for monitoring efficacy and safety or predicting which patients are more likely to respond to a drug or develop adverse events.

Data generated from RBR samples will be analyzed in the context of this study but may also be explored in aggregate with data from other studies. The availability of a larger dataset will assist in identification and characterization of important biomarkers and pathways to support future drug development.

For sampling procedures, storage conditions, and shipment instructions, see the laboratory manual.

All RBR samples are to be stored until they are no longer needed or until they are exhausted. However, the RBR storage period will be in accordance with the IRB/EC-approved Informed Consent Form and applicable laws (e.g., health authority requirements).

4.6.9.4 Confidentiality

All RBR samples and associated data will be labeled with a unique patient identification number.

Patient medical information associated with RBR samples is confidential and may be disclosed to third parties only as permitted by the Informed Consent Form (or separate authorization for use and disclosure of personal health information) signed by the patient, unless permitted or required by law.

Given the complexity and exploratory nature of the analyses of RBR samples, data derived from these analyses will generally not be provided to investigators or patients

unless required by law. The aggregate results of any conducted research will be available in accordance with the effective Sponsor policy on study data publication.

Data generated from RBR samples must be available for inspection upon request by representatives of national and local health authorities, and Sponsor monitors, representatives, and collaborators, as appropriate.

Any inventions and resulting patents, improvements, and/or know-how originating from the use of the RBR data will become and remain the exclusive and unburdened property of the Sponsor, except where agreed otherwise.

4.6.9.5 Consent to Participate in the Research Biosample Repository

The Informed Consent Form will contain a separate section that addresses participation in the RBR. The investigator or authorized designee will explain to each patient the objectives, methods, and potential hazards of participation in the RBR. Patients will be told that they are free to refuse to participate and may withdraw their consent at any time and for any reason during the storage period. A separate, specific signature will be required to document a patient's agreement to provide optional RBR samples. Patients who decline to participate will not provide a separate signature.

The investigator should document whether or not the patient has given consent to participate and (if applicable) the date(s) of consent, by completing the RBR Research Sample Informed Consent eCRF.

In the event of an RBR participant's death or loss of competence, the participant's samples and data will continue to be used as part of the RBR research.

4.6.9.6 Withdrawal from the Research Biosample Repository

Patients who give consent to provide RBR samples have the right to withdraw their consent at any time for any reason. After withdrawal of consent, any remaining samples will be destroyed or will no longer be linked to the patient. However, if RBR samples have been tested prior to withdrawal of consent, results from those tests will remain as part of the overall research data. If a patient wishes to withdraw consent to the testing of his or her RBR samples during the study, the investigator must inform the Medical Monitor in writing of the patient's wishes through use of the appropriate RBR Subject Withdrawal of Informed Consent eCRF. If a patient wishes to withdraw consent to the testing of his or her RBR samples after closure of the study, the investigator must inform the Medical Withdrawal of Informed Consent eCRF. If a patient wishes to withdraw consent to the testing of his or her RBR samples after closure of the study, the investigator must inform the Medical Withdrawal of lnformed Consent eCRF. If a patient wishes to withdraw consent to the testing of his or her RBR samples after closure of the study, the investigator must inform the Sponsor by emailing the study number and patient number to the following email address:

[contact]

A patient's withdrawal from this study does not, by itself, constitute withdrawal of consent for testing of RBR samples. Likewise, a patient's withdrawal of consent for testing of RBR samples does not constitute withdrawal from this study.

4.6.9.7 Monitoring and Oversight

All RBR samples will be tracked in a manner consistent with Good Clinical Practice by a quality-controlled, auditable, and appropriately validated laboratory information management system, to ensure compliance with data confidentiality as well as adherence to authorized use of samples as specified in this protocol and in the Informed Consent Form. Sponsor monitors and auditors will have direct access to appropriate parts of records relating to patient participation in the RBR for the purposes of verifying the data provided to the Sponsor. Site will permit monitoring, audits, IRB/EC review, and health authority inspections by providing direct access to source data and documents related to the RBR samples.

4.7 TREATMENT, PATIENT, AND STUDY DISCONTINUATION

Patients will continue on study treatment until disease progression, discontinuation, withdrawal of consent, or death, whichever occurs first.

Treatment beyond radiological progression is possible in the event of isolated lesion progression if, in the investigator's opinion, there is evidence of ongoing clinical benefit.

In the event of a patient's voluntary withdrawal of consent, the investigator will make a reasonable effort to document the reported reason for consent withdrawal in the eCRF. All efforts will be made to complete the assessments prior to study withdrawal, as detailed in the protocol.

For patients whose status is unclear because they fail to communicate with the study personnel without confirming discontinuation or withdrawal, study personnel will show due diligence by documenting all actions taken to contact the patient (e.g., dates of telephone calls, registered letters, etc.).

Patients will not be considered as lost to follow-up until due diligence has been completed or until the end of the study.

4.7.1 Study Treatment Discontinuation

Patients must permanently discontinue study treatment if they experience any of the following:

- Any medical condition that the investigator or Sponsor determines may jeopardize the patient's safety if he or she continues to receive study treatment
- Investigator or Sponsor determination that treatment discontinuation is in the best interest of the patient
- Pregnancy

Alectinib—F. Hoffmann-La Roche Ltd 65/Protocol BO41929, Version 4

- Use of an anti-cancer therapy not required per protocol
- Symptomatic deterioration attributed to disease progression
- Any event that meets stopping criteria defined in Section 5.1.2

The primary reason for study treatment discontinuation should be documented on the appropriate eCRF. Patients who discontinue study treatment prematurely will not be replaced. Patients with ALK-fusion tumors who are enrolled in the study and do not receive any dose of study treatment will be replaced.

The mHCP will perform a treatment discontinuation visit 28 days after the final dose of alectinib for safety assessments as described in the schedule of activities (see Appendix 1).

If alectinib is prematurely discontinued for reasons other than disease progression, off-treatment disease assessments must continue until radiological progression of the disease as per schedule of activities (see Appendix 1). Following progression, patient status, and subsequent therapies will be captured as long-term follow-up every 3 months until death, patient withdrawal of consent, or termination of the study, whichever occurs first.

4.7.2 Patient Discontinuation from the Study

Patients have the right to voluntarily withdraw from the study at any time for any reason. In addition, the investigator has the right to withdraw a patient from the study at any time.

Reasons for patient discontinuation from the study may include, but are not limited to, the following:

- Patient withdrawal of consent
- Study termination
- Adverse event
- Patient loss to follow-up
- Patient non-compliance, defined as failure to comply with protocol requirements as determined by the investigator or Sponsor

Every effort should be made to obtain a reason for patient discontinuation from the study. The primary reason for discontinuation from the study should be documented on the eCRF.

Patients who wish to discontinue alectinib prematurely remain in the study. If patients wish to stop scheduled assessments after alectinib discontinuation, they will be asked to be contacted regularly for long-term follow-up.

If a patient requests to be withdrawn from the study completely, this request must be documented in the source documents and signed by the investigator. Patients who withdraw from the study will not be replaced.

If a patient withdraws from the study, the study staff may use a public information source (e.g., county records) to obtain information about survival status.

4.7.3 Study Discontinuation

The Sponsor has the right to terminate this study at any time. Reasons for terminating the study may include, but are not limited to, the following:

- The incidence or severity of adverse events in this or other studies indicates a potential health hazard to patients
- Patient enrollment is unsatisfactory

The Sponsor will notify the investigator if the Sponsor decides to discontinue the study.

4.7.4 Site Discontinuation

The Sponsor has the right to close a site at any time. Reasons for closing a site may include, but are not limited to, the following:

- Excessively slow recruitment
- Poor protocol adherence
- Inaccurate or incomplete data recording
- Non-compliance with the ICH guideline for Good Clinical Practice
- No study activity (i.e., all patients have completed the study and all obligations have been fulfilled)

5. ASSESSMENT OF SAFETY

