Response will be assessed by the investigator on the basis of the CT and MRI scans according to RECIST v1.1 (see Appendix 5) or, for patients with primary CNS tumors, RANO criteria, which include neurological examination and corticosteroid use (see Appendix 6).

In addition, scans will be sent for BICR for assessment of responses according to RECIST v1.1 and, for patients with primary CNS tumors, according to RANO criteria.

Assessments performed by BICR will not be shared with the investigator and will have no impact on the management of the patient.

Tumor assessments performed as standard-of-care prior to obtaining informed consent and within 28 days prior to the first dose may be considered as baseline assessment if they satisfy the protocol criteria.

Scheduled tumor assessments should be kept according to the original scheduled based on the date of first dose administration, regardless of clinical visits delays and drug interruptions. At the investigator's discretion, tumor assessment may be repeated at any time if progressive disease is suspected (for example, in case of symptomatic deterioration).

An objective response should be confirmed by repeat assessments at least 4 weeks after initial documentation. No additional assessment is planned for 4 weeks after the initial response, but every effort should be made to obtain confirmation of response, even if a patient who has initially responded is withdrawn from study treatment for any reasons other than progression or death.

Patients who discontinue study treatment for any reason other than progression of disease or death should continue to have regular disease assessments every 8 weeks per the schedule of assessments (see Appendix 1) until progression.

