Appendix 1: Schedule of Activities

CPK = creatine phosphokinase; CT = computed tomography (scan); eCRF = electronic Case Report Form; ECOG = Eastern Cooperative Oncology Group; FFPE = formalin fixed, paraffin embedded; FMI = Foundation Medicine, Inc.; GGT = gamma-glutamyl transferase; MRI = magnetic resonance imaging; NA = not applicable; NGS = next-generation sequencing; PD = progressive disease; PK = pharmacokinetic; PRO = patient-reported outcome; Q2W = every 2 weeks; Q4W = every 4 weeks; Q8W = every 8 weeks; RBR = Research Biosample Repository; SFU = survival follow-up; Tx = treatment; WES = whole exome sequencing; WGS = whole genome sequencing.

Notes: Results of laboratory tests and ECG performed within 3 days before first dose of study drug can be used as baseline assessments.

- ^a Treatment beyond radiological progression is possible in the event of isolated lesion progression if in the investigator's opinion there is evidence of ongoing clinical benefit. For patient receiving study drug beyond radiological progression, scheduled visits (including disease assessments) will continued to be performed until treatment discontinuation.
- ^b For patients who discontinue study treatment prematurely for reasons other than disease progression, tumor assessments should continue until progression.
- c Required follow-up information (e.g., survival status and information on further cancer therapies and procedures [radiotherapy, surgery]) will be collected via telephone calls every 3 months (±14 days) until death, loss to follow-up, or study termination by the Sponsor. More frequent calls may be required when clinical data cut-offs are performed.
- ^d Complete physical examination (head, eyes, ears, nose, and throat, and the cardiovascular, dermatologic, musculoskeletal, respiratory, gastrointestinal, genitourinary, and neurologic systems). Baseline and post-baseline visits: limited physical examination, symptom-directed, and as clinically indicated. For patients with primary CNS tumors, a neurological examination must be performed at each tumor assessment visit and compared with the neurological examination performed at the time of the last disease assessment.
- ^e Coagulation includes PT (or INR) and aPTT (or PTT).
- ^f Includes WBC count, RBC count, hemoglobin, hematocrit, platelet count, and differential count (neutrophils, eosinophils, basophils, monocytes, lymphocytes).

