## 5.4.2 Supportive Secondary Endpoints

## 5.4.2.1 Duration of Response

DOR is defined as the time from the date of the first occurrence of a CR or a PR (whichever status is recorded first) to the date of the first documented disease progression or death due to any causes, whichever occurred first. The DOR will be assessed in patients who had a confirmed objective response during the study, as determined by the investigator or BICR per RECIST v1.1. Patients who have not progressed or died at the time of analysis will be censored at the last tumor assessment date. If no tumor assessments are performed after the date of the first occurrence of a CR or a PR, DOR will be censored at the date of the first occurrence of a CR or a PR. The Kaplan-Meier methodology will be used to estimate the median DOR and to construct survival curves. The Brookmeyer-Crowley methodology will be used to construct the 95% CI for the median DOR (Brookmeyer and Crowley 1982).

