# 5.4.2.2 Progression-Free Survival

Progression free survival is defined as the time from the first date of treatment to the date of first documented disease progression or death, whichever occurs first. Disease progression will be assessed by the investigator or the BICR using RECIST v1.1. Patients who have not experienced disease progression or died at the time of analysis will be censored at the last tumor assessment date. Patients with no post-baseline tumor assessment will be censored at the first date of treatment. The analysis methods are the same as for the DOR defined above.

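### Patients can stop scans yet stay in survival follow-up, and the PFS and DOR rules count their late deaths as events while censoring survivors at the last scan, which can bias PFS in either direction

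*Protocol*

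**What the plan says.** The default is that scans go on after treatment stops. Protocol Section 4.7.1 says that "off-treatment disease assessments must continue until radiological progression of the disease as per schedule of activities", and Section 4.6.5 says that such patients "should continue to have regular disease assessments every 8 weeks per the schedule of assessments".

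Section 4.7.2 then allows an exception: "If patients wish to stop scheduled assessments after alectinib discontinuation, they will be asked to be contacted regularly for long-term follow-up". Survival information "will be collected via telephone calls every 3 months (±14 days) until death, loss to follow-up, or study termination by the Sponsor" (Appendix 1, footnote on long-term follow-up). After full withdrawal, "the study staff may use a public information source (e.g., county records) to obtain information about survival status".

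SAP Section 5.4.2.2 defines PFS as the "time from the first date of treatment to the date of first documented disease progression or death, whichever occurs first". It adds: "Patients who have not experienced disease progression or died at the time of analysis will be censored at the last tumor assessment date". SAP Section 5.4.2.1 has the same event rule for DOR, and: "Patients who have not progressed or died at the time of analysis will be censored at the last tumor assessment date". Neither section limits the time between last scan and death, and neither has a rule for missed scans. The only sensitivity analysis named for these endpoints is the BICR version (SAP Section 5.1), which uses the same event and censoring rule.

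**The concern.** Take two patients who stop scans on the same day without documented progression. One dies before the cut-off. All the time up to death counts as progression-free, although nobody was looking for progression. The other is alive at the cut-off and leaves the risk set at the last scan. Membership of the Kaplan-Meier risk set after the last scan is thus decided by a later outcome, which independent censoring does not allow.

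A DOR example: PR at week 8, confirmed at week 16, last scan at week 24, alectinib and scans stopped at month 6. If the patient dies at month 30, DOR is an event at 30 − 1.8 = 28.2 months (8 weeks = 1.8 months). If the patient is alive at the cut-off, DOR is censored at 24 − 8 = 16 weeks, or 3.7 months.

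At stake is how far the PFS and DOR curves can be trusted as support for a single-arm response rate. In the planning scenario of 23 responders among 50, one such patient is 1/23 = 4.3% of the DOR set.

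**Working it through.** **No planned figure to reproduce.** The documents give no assumed median, event count or stopping rate for PFS or DOR. Direction and size were therefore checked by simulation of PFS, with 400,000 patients per scenario.

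**The rule.** Let P be the date of documented progression, D death, L the last scan and C the cut-off. If P is observed, the event is at P. If not, and D ≤ C, the event is at D. Otherwise the patient is censored at L. The time from L to D counts only when D ≤ C.

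**Two opposing effects.**
- Upward: an unseen progression is dated at the later death.
- Downward: after L only patients who go on to die stay at risk, so the event rate there is inflated.

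As follow-up matures, nearly all stoppers have died. Their PFS curve becomes their survival curve, and the upward effect wins.

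**Inputs.** From the documents: 8-weekly scans with a ±5-day window, 24-week minimum follow-up at the primary analysis, and the event and censoring rules. Assumed: exponential progression with median 10 months; median survival of 12 months after progression; death without progression 0.5% a month; 24 months' accrual. Scans stop either at random between months 2 and 10 (unrelated) or in the 4 months before progression (near). The 24-week minimum gives a cut-off at 24 + 5.5 = 29.5 months.

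**Check of the full-scanning value.** The last scan before month 12 is at week 48 (11.04 months): 2^(−11.04/10) × e^(−0.005×12) = 0.465 × 0.942 = 43.8%. Before month 24 it is week 104 (23.92 months): 0.1905 × 0.887 = 16.9%. The simulation gives 43.7% and 16.9%.

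**Results: PFS in %, 12 months / 24 months** (a dash means not tabulated; separate runs differ by up to 0.2 points)

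| Stopping | Cut-off (month) | Full scanning | Planned rule | Censor if gap >117 days | Date at next scan |
|---|---|---|---|---|---|
| Unrelated, 14% | 60 | 43.7 / 16.9 | 46.3 / 19.8 | 43.3 / 16.7 | 36.8 / – |
| Unrelated, 28% | 60 | 43.7 / 16.9 | 49.1 / 23.0 | 42.8 / 16.5 | – |
| Unrelated, 13% | 29.5 | 43.7 / 16.7 | 43.6 / 14.9 | – | – |
| Unrelated, 27% | 29.5 | – / 16.8 | – / 12.8 | – | – |
| Near, 18% | 60 | 43.8 / – | 50.4 / – | 49.2 / – | 43.4 / – |
| Near | 29.5 | 43.6 / 16.7 | 48.3 / 18.5 | 49.0 / 21.5 | – |

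Planned rule minus full scanning:
- Month 60, unrelated: 46.3 − 43.7 = +2.6 and 49.1 − 43.7 = +5.4 points at 12 months; +2.9 and +6.1 at 24 months.
- Month 29.5, unrelated: −0.1 at 12 months; 14.9 − 16.7 = −1.8 and 12.8 − 16.8 = −4.0 at 24 months.
- Near progression: 50.4 − 43.8 = +6.6 at month 60 and 48.3 − 43.6 = +4.7 at month 29.5, both at 12 months.

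In between (36 months' accrual, cut-off at month 42, unrelated stopping), 12-month PFS is 44.4% with 13.6% stopping and 45.1% with 27.0%, against 43.7%. In a close variant (month 41.5), 24-month PFS is 16.5% against 16.8%.

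**Other assumptions.** Median progression / post-progression survival was set to 8/8, 12/12 and 8/16 months, with 10%, 20% or 30% stopping. Change in 12-month PFS under the planned rule:
- Unrelated stopping at primary-analysis timing: −0.5 to +0.1 points.
- Unrelated stopping with at least 36 months' follow-up: +0.9 to +6.4 points.
- Stopping in the 0 to 4 months before progression, either follow-up: +2.0 to +11.5 points.

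**The case against.** The strongest reply is that the rule follows from the definition. Both endpoints count death from any cause, so counting every death is defensible. Scans off treatment are mandatory until progression, and Section 4.7.2 is a narrow exception whose use nobody can quantify; the rates of 14% and 28% are assumptions. PFS and DOR are supportive secondary endpoints without a test or threshold. SAP Section 5.2 also summarises patient status and time of efficacy follow-up, so scan attrition would be partly visible. All of this stands. It argues for leaving the main definition alone and for keeping the point in proportion.

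It does not remove the point. The BICR analysis cannot show the effect, because it shares the rule and the missing scans. The gap is wider there: scans may end at investigator-assessed progression, so a patient without BICR progression who dies later has a BICR event on the date of death. Stopping near progression is plausible, since Section 4.7.1 makes symptomatic deterioration attributed to progression a reason to stop treatment and sets no scan as a condition.

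A reader might infer that the rule overstates both PFS and DOR. The documents do not support that. The one non-interim efficacy analysis whose timing they fix is the primary one, and there, with stopping unrelated to progression, 24-month PFS is understated. The roughly 5 years in Protocol Section 3.2 is the length of the study including accrual, not follow-up per patient, and no month-60 PFS or DOR analysis is specified. DOR was not simulated.

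**Conclusion.** The concern holds in a limited form. The text allows scans to stop while survival is still collected, and the event and censoring rules then make time at risk after the last scan depend on a future death. PFS can be biased either way: upward with mature follow-up or when scans stop shortly before progression; roughly neutral at 12 months and about 2 to 4 points low at 24 months at the primary analysis when stopping is unrelated to progression.

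All sizes rest on assumed progression, survival, accrual and stopping patterns. If few patients stop scans, the effect is small. DOR has the same mechanism, but its size is unknown. Confirmed ORR is unaffected: it does not use these rules, and a patient without confirmation is a non-responder. What is missing is a pre-specified way to see whether the problem occurred and how much it matters.

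**What to change.** Keep the main definitions. Add to SAP Sections 5.4.2.1 and 5.4.2.2, for both investigator and BICR:

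- (a) A sensitivity analysis in which a death more than 117 days after the last evaluable scan is censored at that scan (2 × 56 + 5 = 117: two 8-week intervals plus the 5-day window).
- (b) A companion analysis in which such a death is an event dated at the next scheduled scan after the last evaluable one.
- (c) The number of deaths affected, for each endpoint and assessor.

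The cost is a few sentences and some extra Kaplan-Meier outputs.

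Neither analysis is sufficient alone. With unrelated stopping, (a) stays within about 1 point of full scanning. If scans stop because progression is near, (a) remains too high and can exceed the main analysis (49.0% against 48.3%, full scanning 43.6%). Analysis (b) is close to full scanning for near-progression stopping at month 60 (43.4% against 43.8%), but too low when 14% stop for unrelated reasons (36.8% against 43.7%). The two should be read together as a range, not as guaranteed bounds: (b) re-dates only deaths, so at an early cut-off stoppers still alive remain censored at their last scan. If (c) is zero or near zero, the question largely closes.
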